#### 4.1.4.2 Dose reductions and dose delays

For the assessment of the severity of adverse events (AEs), CTCAE version 5 ([R18-1357](#)) will be used. Any SAEs/AEs of  $\geq$ Grade 2 deemed intolerable by the patient or the treating physician and not responding to appropriate medical management, and any related SAEs/AEs of  $\geq$ Grade 3 will result in the interruption of treatment with BI 3011441 until resolution to baseline or Grade 1. Please see [section 3.3.4.1](#) for the permanent IMP discontinuation criteria.

Proprietary confidential information © 2020 Boehringer Ingelheim International GmbH or one or more of its affiliated companies

If the treatment interruption is  $\leq 2$  weeks, the patient can be re-exposed to BI 3011441 at the same dose or one dose level lower than the dose administered before the interruption as long as the re-exposure is considered clinically indicated by the Investigator. However, dose reduction is not allowed for patient who uses 4 mg, and the study medication (BI 3011441) needs to be discontinued.

In case the treatment is delayed due to an AE, the patient should visit the site at least once a week for assessment of safety laboratory and AEs. More frequent visits may be appropriate as assessed by the Investigator. Any case of a delay in treatment cycle for more than 2 weeks should be communicated to the Sponsor. The Investigator in agreement with the Sponsor will decide about further treatment of individual patient, based on known risk/benefit of BI 3011441.

A maximum of 1 dose reductions of BI 3011441 are allowed, if lower tested dose levels are available. Dose reductions will be only to doses previously explored in earlier cohorts.

In case of dose reductions, all future dose administrations will also be at the reduced dose level. If that is intolerable (as previously described), the treatment of that patient should be discontinued. Recommendations for dose reductions of BI 3011441 are given in [Tables 4.1.4.2: 1, 4.1.4.2: 2, and 4.1.4.2: 3](#).

Proprietary confidential information © 2020 Boehringer Ingelheim International GmbH or one or more of its affiliated companies

Table 4.1.4.2: 1

Dose modification for BI 3011441 for haematologic and non-haematologic toxicity related to treatment

Haematologic and non-haematologic toxicity	Dose modification
Grade 1	

Continue BI 3011441 at full dose, monitor as clinically indicated.

Grade 2	

Provide appropriate medical management as clinically indicated.

Consider holding BI 3011441 until resolution to Grade 1 or baseline and resume BI 3011441 at the same dose.

Deemed intolerable by the patient or the treating physician in case of continuation of BI 3011441 and not responding to appropriate medical management, interrupt BI 3011441 until resolution to baseline or Grade 1 and then, resume BI 3011441 at the reduced dose by 1 dose level.

Grade 3 a	

Interrupt BI 3011441 until toxicity is Grade 1 or baseline, and then reduce the dose of BI 3011441 by 1 dose level.

The patient may be continued at the same dose if the toxicity is unequivocally considered to be unrelated to BI 3011441 by the Investigator in agreement with the Sponsor.

Continue monitoring as clinically indicated and provide appropriate medical management as needed.

Grade 4 a	

Discontinue BI 3011441.

Continue monitoring as clinically indicated and provide appropriate medical management as needed.

a If the patient has a Grade 3 or 4 laboratory abnormality that, in the judgement of the investigator, is not considered clinically significant, dose modification is not required.

Table 4.1.4.2: 2 Dose modification for retinopathy in BI 3011441

Adverse event	Dose modification
Grade 1	

• Immediately refer to the patient for ophthalmologic exam (if an ophthalmologic exam cannot be performed within 7 days, interrupt BI 3011441).

• If an ophthalmologic exam is done within 7 days and no worsening, continue BI 3011441 and monitor as clinically indicated.

• If retinopathy worsens to Grade 2 or 3, see below for guidance.

Grade 2 or Grade 3	

• Immediately refer to the patient for ophthalmologic exam.

• Interrupt BI 3011441 until resolution to baseline or Grade 1 and then, resume BI 3011441 at the reduced dose by one dose level.

• Continue monitoring as clinically indicated and provide appropriate medical management as needed.

Grade 4	

• Immediately refer to the patient for ophthalmologic exam.

• Permanently discontinue BI 3011441.

• Continue monitoring as clinically indicated and provide appropriate medical management as needed.

Table 4.1.4.2: 3 Dose modification for LVEF decrease in BI 3011441

Adverse event	Dose modification
Grade 1	

• Not applicable

Grade 2 a	

• Interrupt BI 3011441 until resolution to the normal institutional range or to within 5 percentage points of the baseline value and then, resume BI 3011441 at the reduced dose by one dose level.

• Continue monitoring as clinically indicated and provide appropriate medical management as needed.

Grade 3 and 4	

• Permanently discontinue BI 3011441.

• Continue monitoring as clinically indicated and provide appropriate medical management as needed.

a An absolute decrease in LVEF of 10 percentage points or greater from baseline value to a value that is below institutional LLN value, OR an absolute decrease in LVEF of 15 percentage points or greater and lower than 20 percentage points whether below or above institutional LLN value

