#### 5.2.6.1.5 Intensity (severity) of AEs

The intensity (severity) of adverse events should be classified and recorded in the CRF according to the CTCAE version 5.0 ([R18-1357](#)).

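### Table 4.1.4.2: 3 footnote a: the first limb of the Grade 2 LVEF definition lacks the 20-point cap of the second, so a large fall to below normal literally lands in the row that permits restart

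*Protocol*

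**What the plan says.** Protocol Section 4.1.4.2, Table 4.1.4.2: 3, sets the action for an LVEF decrease by grade. Footnote a defines Grade 2 by either of two limbs:

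- Limb 1: "An absolute decrease in LVEF of 10 percentage points or greater from baseline value to a value that is below institutional LLN value".
- Limb 2: a fall of 15 "percentage points or greater and lower than 20 percentage points whether below or above institutional LLN value".

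The Grade 2 action is "Interrupt BI 3011441 until resolution to the normal institutional range or to within 5 percentage points of the baseline value", then resume one dose level lower. The combined Grade 3 and 4 row says "Permanently discontinue BI 3011441". It carries no numeric criterion and no footnote.

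The grading scale is named elsewhere. Section 4.1.4.2 opens with "For the assessment of the severity of adverse events (AEs), CTCAE version 5", and Section 5.2.6.1.5 says that intensity "should be classified and recorded in the CRF according to the CTCAE version 5.0". The text of CTCAE v5 is not in the documents. No sentence says which governs if the footnote and CTCAE v5 give different grades.

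Two limits on dose reduction matter here: "dose reduction is not allowed for patient who uses 4 mg" (the drug is discontinued instead), and "A maximum of 1 dose reductions of BI 3011441 are allowed, if lower tested dose levels are available".

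**The concern.** Limb 2 stops at 20 points on both sides of LLN, so the footnote appears meant to keep larger falls out of the Grade 2 row wherever they end. Limb 1 undoes that for falls ending below LLN. The anomaly runs in the unsafe direction: of two patients with the same fall of 20 points or more, the one left below normal is placed in the row that allows re-treatment, and the one still within normal is not.

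The same two limbs appear without a cap in the new-cycle criteria (4.1.4.1) and in the LVEF DLT item (5.2.6.3). There they act as minimum triggers and need no ceiling. In footnote a they mark a grade band, and only one limb received the ceiling.

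At stake is whether a patient who had a fall of that size and has recovered may be re-exposed, and whether sites would decide this in the same way. Other text gives little help for an asymptomatic Grade 3 fall that recovers. The permanent-discontinuation list in 3.3.4.1 does not name it, and the general Grade 3 row in Table 4.1.4.2: 1 allows restart at a reduced dose. The LVEF table is the only explicit instruction to stop, and its boundary is unclear.

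**Working it through.** There is no plan figure to reproduce. The check treats footnote a as a logical rule.

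**Inputs.** Screening LVEF is at least 50% (exclusion criterion 9, Section 3.3.3). The limits of 10, 15 and 20 points come from footnote a. LLN is institutional and not given, so 50%, 53% and 55% are assumed.

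**Rule.** Let d be the fall in points, v the on-treatment value and L the LLN.

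- Limb 1: d ≥ 10 and v < L.
- Limb 2: 15 ≤ d < 20.
- Grade 2: limb 1 or limb 2.

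**What limb 1 adds.** Limb 2 already covers 15 ≤ d < 20 on both sides of LLN. Limb 1 therefore adds two groups: 10 ≤ d < 15 with v < L, and d ≥ 20 with v < L. The second group is the problem.

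**Examples, L = 50%.**

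| Screening to on-treatment | Fall | Grade 2 as written? |
|---|---|---|
| 65% to 43% | 22 | yes, limb 1 |
| 69% to 49% | 20 | yes, limb 1 |
| 70% to 50% | 20 | no |
| 73% to 51% | 22 | no |

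**Which patients are exposed.** Every fall of 20 points or more ends below LLN when screening LVEF is below L + 20. In whole percentages that is 50–69% (L = 50), 50–72% (L = 53) or 50–74% (L = 55).

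**Effect of a cap.** Take integer screening values 50–80% and falls of 1–40 points: 31 × 40 = 1240 pairs, of which 31 × 21 = 651 have d ≥ 20 and 31 × 19 = 589 have d < 20. At L = 50, the pairs with d ≥ 20 and v ≥ L come from screening values 70–80% and number 1 + 2 + … + 11 = 66.

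| Assumed LLN | d ≥ 20, not Grade 2 as written | d ≥ 20, Grade 2 as written | d ≥ 20, Grade 2 with cap | d < 20, changed by cap |
|---|---|---|---|---|
| 50% | 66 | 651 − 66 = 585 | 0 | 0 of 589 |
| 53% | 36 | 651 − 36 = 615 | 0 | 0 of 589 |
| 55% | 21 | 651 − 21 = 630 | 0 | 0 of 589 |

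These counts describe how the rule behaves on a chosen grid. They are not probabilities.

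**DLT consequence (5.2.6.3).** A related fall at the Cycle 1 Day 15 echo generally counts already. Restart at a lower dose within Cycle 1 is a dose reduction in Cycle 1. A hold from Day 15 to Day 28 lasts 28 − 15 + 1 = 14 days and meets the item for a pause of at least 14 days. From Day 16, the window edge, the hold is 13 Cycle 1 days.

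The Cycle 2 Day 1 echo also counts for the MTD. A related Grade 2 or higher toxicity that persists and delays dosing on that day by more than 2 weeks is a DLT under either row. That leaves mainly falls first seen at that echo that recover within about 2 weeks. These can count through the item for events requiring permanent discontinuation if the Grade 3 and 4 row applies, through a Grade 3 or higher item if graded so, or as another toxicity confirmed by the SMC.

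**The case against.** The strongest reply is that the rows are labelled by grade and CTCAE v5 is the named scale. A site that grades by CTCAE v5 first would use the Grade 3 and 4 row if CTCAE v5 calls the fall Grade 3, and the footnote would never decide the case. This has force, but the footnote prints its own Grade 2 definition and the protocol gives no precedence rule, so the ambiguity remains.

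The second reply is that other text narrows the effect, and this stands:

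- Drug is interrupted under either row, and the Grade 2 row allows restart only after recovery.
- Symptomatic heart failure and drug-related Grade 4 events already mean permanent discontinuation (3.3.4.1).
- Restart rests with the investigator alone only for interruptions of up to 2 weeks. After a longer delay it needs sponsor agreement (4.1.4.2).
- Interruption of more than 4 weeks due to an adverse event means discontinuation, except in justified cases agreed in writing with the sponsor (3.3.4.1).
- At 4 mg, or after the one permitted reduction, drug stops anyway.
- The protocol calls the tables recommendations.

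The third reply is that a Grade 3 and 4 criterion of 20 points or more is only inferred from limb 2's cap. That is also right. The documents do not show that fall size is the sole criterion or that one cut-off serves both grades.

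A reader might infer that the protocol puts such patients in two rows with incompatible actions, or directs that Grade 3 falls be re-treated. The documents do not support this: the overlap exists only if CTCAE v5 grades these falls as 3 or 4, and that text is not available here.

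**Conclusion.** Footnote a is internally inconsistent and wrong as written; severity is low. That limb 1 lacks the cap follows from the printed text alone. What a site would do with such a patient depends on CTCAE v5 and on which source the site lets prevail.

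The affected patient is asymptomatic, on 6, 7 or 8 mg (3 of the 4 provisional levels), not yet dose-reduced, and has recovered after a fall of 20 points or more to below LLN. About 12 patients are planned. The documents give no frequency of such falls, no LLN and no distribution of screening LVEF, so no rate is claimed. The screening ranges in the working depend on the assumed LLN.

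A reader might also infer that MTD determination is compromised. The documents do not support that: most related falls of this size reach the DLT count by other items, and the remaining gap is mainly a quickly recovered fall first seen at Cycle 2 Day 1.

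**What to change.** 1. In footnote a, give limb 1 the same upper limit as limb 2: a fall of less than 20 points.
2. Add one sentence: LVEF falls outside footnote a are graded by CTCAE v5, and if more than one row applies, the row for the higher grade governs. Without this, the cap alone would leave falls of 20 points or more in no printed row.
3. Print a numeric Grade 3 and 4 criterion only after the sponsor has verified it against CTCAE v5.
4. Leave the LVEF DLT item in 5.2.6.3 unchanged.

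The cost is one phrase and one sentence, with no new assessments. There are two downsides. A few patients with a recovered fall of 20 points or more may lose the option to resume at a lower dose. A related fall of that size at Cycle 2 Day 1 may also count as a DLT through the existing permanent-discontinuation item, which touches the primary endpoint and should be acknowledged in the amendment rationale.

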#### **4.1.5 Blinding and procedures for unblinding**

##### **4.1.5.1 Blinding**

This phase I trial will be handled in an open fashion by the Sponsor throughout, i.e., also for the purpose of data cleaning and preparation of the analysis. The CRF will contain information on the treatment and the dose.

##### **4.1.5.2 Unblinding and breaking the code**

Not applicable.

#### **4.1.6 Packaging, labelling, and re-supply**

The investigational medicinal products will be provided by BI or a designated Contract Research Organisation (CRO). They will be packaged and labelled in accordance with the principles of Good Manufacturing Practice (GMP). Re-supply to the sites will be managed via an IRT system, which will also monitor expiry dates of supplies available at the sites. For details of packaging and the description of the label, refer to the ISF.

#### **4.1.7 Storage conditions**

Drug supplies will be kept in their original packaging and in a secure limited access storage area according to the recommended storage conditions on the medication label. A temperature log must be maintained for documentation.

If the storage conditions are found to be outside the specified range, the Clinical Research Associate (CRA) (as provided in the list of contacts) must be contacted immediately.

#### **4.1.8 Drug accountability**

The investigator or designee will receive the investigational drugs delivered by the sponsor when the following requirements are fulfilled:

- Approval of the clinical trial protocol by the IRB / ethics committee.
- Availability of a signed and dated clinical trial contract between the sponsor and the investigational site.
- Approval/notification of the regulatory authority, e.g. competent authority.
- Availability of the curriculum vitae of the Principal Investigator.
- Availability of a signed and dated clinical trial protocol.

Investigational drugs are not allowed to be used outside the context of this protocol. They must not be forwarded to other investigators or clinics. Patients should be instructed to return unused investigational drug.

The investigator or designee must maintain records of the product's delivery to the trial site, the inventory at the site, the use by each patient, and the return to the sponsor or warehouse / drug distribution centre or alternative disposal of unused products. If applicable, the sponsor or warehouse / drug distribution centre will maintain records of the disposal.

These records will include dates, quantities, batch / serial numbers, expiry ('use- by') dates, and the unique code numbers assigned to the investigational medicinal product and trial patients. The investigator or designee will maintain records that document adequately that the patients were provided the doses specified by the Clinical Trial Protocol (CTP) and reconcile all investigational medicinal products received from the sponsor. At the time of return to the sponsor, the investigator or designee must verify that all unused or partially used drug supplies have been returned by the clinical trial patient and that no remaining supplies are in the investigator's possession.

## **4.2 OTHER TREATMENTS, EMERGENCY PROCEDURES, RESTRICTIONS**

### **4.2.1 Other treatments and emergency procedures**

There are no special emergency procedures to be followed.

Rescue medications to reverse the actions of BI 3011441 are not available. Adverse events should be treated symptomatically and must be recorded. Concomitant medications or therapy to provide adequate supportive care may be given as clinically necessary

### **4.2.2 Restrictions**

#### **4.2.2.1 Restrictions regarding concomitant treatment**

Concomitant therapy, with reasons for the treatment, must be recorded in the CRF during the screening and treatment periods, starting at the date of signature of informed consent and ending after the REP. After REP, only concomitant therapy indicated for treatment of a related AE has to be reported. If a new anti-cancer treatment is started, it will be documented in the CRF on a separate page of follow-up therapy, different from the concomitant therapies pages.

No anticancer therapy (including regular use of steroids exceeding 10 mg daily prednisone or equivalent) can be administered during treatment with BI 3011441. No other investigational drug must be used concomitantly with the study drug, and the patients are not allowed to participate concurrently in any other clinical study.

The use of concomitant medications that might lead to QT prolongation is prohibited and would require the discontinuation of the patient prior to starting the respective QT prolonging medication.

Pre-medications (e.g. antiemetics for nausea or vomiting) should not be given in cycle 1 to avoid masking the emergence of DLTs.

Prophylactic granulocyte colony stimulating factors are not allowed during the first 4 weeks of treatment

Proprietary confidential information © 2020 Boehringer Ingelheim International GmbH or one or more of its affiliated companies

For symptom control, palliative radiotherapy is permitted for any lesion, except during the DLT evaluation period (e.g. first 4 weeks) for MTD/RD determination. If the palliative radiotherapy is necessary during the MTD determination period (e.g. first 4 weeks), then the patients will be replaced. If the palliative radiotherapy is necessary during the study, a case-by-case decision will be made together with the sponsor. Lesions that have been exposed to radiotherapy are no longer evaluable, and may not be included in the assessment of the non-target lesions and the overall assessment. Study medication needs to be interrupted during the palliative radiotherapy and maybe resumed once the patient has recovered from any radiation associated toxicity. If the medication is interrupted for more than 14 days, the decision to continue with the study medication will be made by the investigator in agreement with the sponsor.

[REDACTED]

[REDACTED] Table 4.2.2.1:1 provides a list of restricted medications. Alternatives with less potential for CYP450 based interactions should be considered, where available. Close monitoring for potential adverse reactions is warranted and patients should be informed about potential signs and symptoms of such adverse reactions (e.g., muscle pain). BI 3011441 was also found to be [REDACTED]

[REDACTED] provides a list of restricted and permitted medications.

Table 4.2.2.1:1

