The Safety Monitoring Committee (SMC, see [Section 8.7](#)) will recommend the size for the next dose escalation cohort. After all patients in a cohort have either experienced a DLT or have been observed for at least the MTD evaluation period without experiencing a DLT, the Bayesian model will be updated with the newly accumulated data. The overdose risk will then be calculated for each dose, and escalation will be permitted to all doses which fulfil the EWOC criterion and the additional 50 % escalation rule. Based on the model and on

Proprietary confidential information © 2020 Boehringer Ingelheim International GmbH or one or more of its affiliated companies

additional information (PK, PD, patient profiles), the members of the SMC will reach a joint decision on the next dose level to be investigated.

If DLTs are observed in the first two consecutive patients of a previously untested dose level, subsequent enrolment to that cohort will be stopped. The BLRM will be re-run to confirm that the dose level still fulfils the EWOC principle. Based on this information, the SMC will evaluate whether the next patients will be enrolled at the same dose level, or if they will be enrolled at a lower dose level.

The SMC may recommend stopping the dose escalation phase after the criterion for MTD ([Section 7.1](#)) is fulfilled. Further patients may be included to confirm this MTD estimate, i.e. to confirm that the EWOC criterion is still fulfilled. If no DLT is observed at a dose of which the efficacy is considered sufficient, the SMC may decide to include an additional number of patients at the same dose level and to declare this dose as the recommended.

The SMC can declare any dose fulfilling the EWOC criterion as the RD, independent of the MTD estimate.

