### 3.3.4.1.2 Replacement of patients

Patients who are not evaluable for the MTD determination will be replaced, and an additional patient will be entered at the same dose level, if not decided otherwise by the SMC (e.g. because the number of evaluable patients for the current dose level is considered high enough for a dose escalation decision).

Patients who permanently discontinue treatment because of a DLT (please see [section 5.2.6.3](#)) will not be replaced.

The following patients may be replaced:

- Patients who have not received any drug after they have signed the informed consent.
- Patients who permanently discontinue treatment during the MTD evaluation period for reasons other than a DLT.
- Patients who have missed more than 8 doses of BI 3011441 during the MTD evaluation period for reasons other than a DLT.
- Patients who miss 2 or more partial or complete visits during the MTD evaluation period and (after discussion between the Sponsor and the Investigator) if the information needed to assess PK/PD and safety parameters (including evaluation for DLTs) is missing, unless they develop a DLT.
- Patient who need palliative radiotherapy during MTD determination period (e.g. first 4 weeks).

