### 7.3.2 Primary endpoint analyses

In order to identify the MTD, the number of evaluable patients with DLTs during the MTD evaluation period at each dose level must be presented. Replaced patients will be excluded from the determination of MTD.

The main analysis of the MTD will use the BLRM model described above using DLT data from the MTD evaluation period.

For the analysis of tolerability and safety, please refer to [Section 7.3.5](#).

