7.8 SAFETY ANALYSIS

All safety analyses will be performed on the treated set. Treated patients will be analyzed according to their initial treatment.

Patients who were replaced within the MTD evaluation period will be excluded from the determination of the MTD in the dose escalation but will be considered for all other safety evaluations.

Safety data recorded during the Residual Effect Period (REP) of 30 days will be considered as on-treatment.

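### The replacement rules for palliative radiotherapy and early discontinuation make no exception for a patient who has already had a DLT, so an observed DLT can leave the MTD determination

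*Protocol*

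**What the plan says.** **Replacement rules.** Protocol 4.2.2.1 is unconditional: "If the palliative radiotherapy is necessary during the MTD determination period (e.g. first 4 weeks), then the patients will be replaced". Section 3.3.4.1.2 lists the same radiotherapy case among patients who may be replaced, together with "Patients who permanently discontinue treatment during the MTD evaluation period for reasons other than a DLT". Its missed-dose bullet also turns on the reason for missing doses.

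**Protection for DLTs in 3.3.4.1.2.** "Patients who permanently discontinue treatment because of a DLT" are not replaced. The missed-visit bullet carries its own exception, for patients whose needed information "is missing, unless they develop a DLT". The radiotherapy and early-discontinuation bullets have no such clause.

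**Effect of replacement.** Protocol 7.3.2: "Replaced patients will be excluded from the determination of MTD". SAP 7.8 agrees: "Patients who were replaced within the MTD evaluation period will be excluded from the determination of the MTD in the dose escalation".

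**Text pointing the other way.** Protocol 5.2.6.3 makes DLTs seen in the MTD evaluation period count towards the MTD, with no carve-out for later events. Protocol 3.1 updates the model "After all patients in a cohort have either experienced a DLT or have been observed for at least the MTD evaluation period" without one, so a DLT completes a patient's observation. SAP 6.3 defines the MTD Set, which feeds the BLRM, as patients who were not replaced, and then adds that replaced patients are included too.

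**The concern.** Take a patient with a DLT on Day 10 who restarts or is holding drug. If a metastasis needs palliative radiotherapy on Day 22, section 4.2.2.1 requires replacement. If the patient instead stops for progression on Day 24, section 3.3.4.1.2 permits it, because the reason for stopping was not the DLT. In both cases 7.3.2 then removes a DLT that has already been observed.

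Two things are at stake. The number of patients with DLTs in the evaluation period is itself a primary endpoint, and 7.3.2 presents it for evaluable patients. The other primary endpoint, the MTD, rests on the EWOC criterion, which 3.1 makes a hard bar to escalation. With about 12 patients planned and at least 6 at the MTD (7.6), one DLT can decide whether that bar applies.

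**Working it through.** **Step 1. The sequence DLT, then a later event, under each provision**

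| Provision | DLT, then radiotherapy in Cycle 1 | DLT, then stop for progression in Cycle 1 |
|---|---|---|
| Protocol 4.2.2.1 | must be replaced | not addressed |
| Protocol 3.3.4.1.2 | may be replaced | may be replaced |
| Protocol 7.3.2, SAP 7.8 | out of MTD determination if replaced | same |
| Protocol 5.2.6.3 | DLT counts | DLT counts |
| Protocol 3.1 | observation complete at the DLT | same |
| SAP 6.3 | set limited to patients not replaced, yet replaced patients included | same |

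The documents do not settle whether the DLT counts. Because the exception is written into the missed-visit bullet, it cannot simply be assumed elsewhere.

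**Step 2. Reproducing the protocol's model**

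Inputs (protocol 7.1 and Table 7.1:2): logit(π_d) = log α + β·log(d/8). The prior on (log α, log β) is a mixture of three normals:
- weight 0.8, mean (−0.94, 0.61), SD (0.91, 0.91), correlation −0.08
- weight 0.1, mean (0.85, 0.79), SD (2, 1), correlation 0
- weight 0.1, mean (−2.20, 0.80), SD (2, 1), correlation 0

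A dose passes EWOC if P(π_d ≥ 0.33) < 0.25. P(OD) below is that probability, found by grid integration.

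| Quantity | Printed | Recomputed |
|---|---|---|
| Prior P(OD) at 4 / 6 / 7 / 8 mg | 0.128 / 0.233 / 0.310 / 0.422 | 0.129 / 0.232 / 0.310 / 0.422 |
| Scenario 7, P(OD) at 6 mg | 0.153 | 0.148 |
| Scenario 20, P(OD) at 8 mg | 0.106 | 0.103 |
| Scenario 21, P(OD) at 8 mg | 0.274 | 0.268 |

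Across the 19 data scenarios run, the current-dose P(OD) was within 0.016 of Table 10.2:1. One scenario not used here (13) falls on the other side of 0.25 (0.259 against a printed 0.243), so only results well clear of the limit are relied on, or results where the printed and recomputed values agree on the side.

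**Step 3. The effect of one lost DLT**

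*8 mg, after 0/3 at 4 mg and 0/3 at 6 mg:*

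| Handling of one of two DLT patients | Data at 8 mg | P(OD) at 8 mg | EWOC at 8 mg |
|---|---|---|---|
| Kept, not replaced (scenario 21) | 2/6 | 0.274 printed, 0.268 recomputed | fails; next dose 7 mg |
| Removed, DLT-free replacement (scenario 20) | 1/6 | 0.106 printed, 0.103 recomputed | passes; 10.2 says the MTD could be declared at 8 mg |
| Removed, no replacement | 1/5 | 0.137 recomputed | passes |
| Kept and a DLT-free patient added (SAP 6.3 wording) | 2/7 | 0.212 recomputed | passes |

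*6 mg, after 0/3 at 4 mg:*

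| Handling of the one DLT patient | Data at 6 mg | P(OD) at 8 mg (recomputed) | Next dose |
|---|---|---|---|
| Kept (scenario 7) | 1/3 | 0.431 | 6 mg |
| Removed, DLT-free replacement (scenario 6) | 0/3 | 0.197 (printed 0.185) | 8 mg |
| Removed, no replacement | 0/2 | 0.223 | 8 mg |
| Kept and a DLT-free patient added | 1/4 | 0.382 | 7 mg |

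The 0/2 row matters because protocol 3.1 allows escalation on two evaluable patients without a DLT. The same clinical events give different model results depending on which sentence is followed.

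**The case against.** **Intent is recoverable.** Section 3.3.4.1.2 opens with patients who are not evaluable, 3.1 treats a DLT as completing observation, and 5.2.6.3 counts it. A reasonable reader would keep the patient. This stands as evidence of intent, but it leaves an unconditional sentence in 4.2.2.1 and the exclusion in 7.3.2 uncorrected. Section 3.1 also does not expressly bar replacement.

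**The exposed group is narrow.** Stopping because of a DLT is protected, and several DLT types require permanent discontinuation (3.3.4.1). At 4 mg, 4.1.4.2 allows no reduction and requires stopping instead, so much of the starting-dose case is protected. What remains is a DLT, then hold or restart, then an unrelated event in the same 28 days. This stands.

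**Discretion and other safeguards.** Replacement is mandatory only for radiotherapy; under 3.3.4.1.2 it is permitted, and the SMC can decide otherwise. The SMC sees adverse events of excluded patients (4.1.2) and decides on more than the model. The model is rerun with all DLTs to inform the recommended dose (2.1.1), and treated-set tables keep the event (SAP 7.8.1.1). All true. None of it restores the DLT to the EWOC calculation that permits or bars escalation.

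**Bias.** A reader might infer that the rules push the MTD upwards because they can only remove DLTs. The documents do not support that. DLT-free patients are replaced for the same events, and a replacement may have a DLT. If those events are independent of DLT, the expected rate is unchanged. Independence can be doubted, since related Grade 3 or higher events interrupt treatment (4.1.4.2), but nothing in the documents measures the dependence.

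**Conclusion.** The rules are wrong as written. Followed literally, 4.2.2.1 with 7.3.2 removes an observed DLT from the MTD determination, and 3.3.4.1.2 allows the same after discontinuation for another reason. This conflicts with 5.2.6.3, and the SAP contradicts itself on whether replaced patients are in the MTD Set.

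The size is conditional. When the situation arises at 8 mg with 2/6 DLTs, P(OD) moves from 0.274 to 0.106 and the EWOC result reverses; at 6 mg with 1/3, the next dose moves from 6 mg to 8 mg. These comparisons assume three-patient cohorts as in 10.2 and a DLT-free replacement. They show sensitivity to one DLT, not that the SMC would overlook a visible event.

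Three stronger readings go beyond the documents: that the MTD is biased upwards, that removal is compulsory in every case, and that a particular share of DLT patients is affected. No rate of Cycle 1 radiotherapy or progression is given, so no frequency can be stated.

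**What to change.** All changes concern membership of the analysis set. None touches whether radiotherapy is given or treatment continues.

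1. Protocol 3.3.4.1.2 and 7.3.2: state that *a patient with a DLT in the MTD evaluation period is evaluable for the MTD and is not replaced, whatever happens afterwards*.
2. Protocol 4.2.2.1: add *unless a DLT has already occurred* to the replacement sentence.
3. SAP 6.3: remove or correct the sentence that brings replaced patients into the MTD Set, so that it agrees with SAP 7.8 and protocol 7.3.2. The protocol edits alone would leave this contradiction in place.

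**Cost.** A few sentences at the next amendment and SAP update. There is a statistical price: keeping DLT patients while replacing DLT-free ones raises the estimated rate slightly. As an illustration, assume a true DLT rate of 0.25, probability q of a replacement event in Cycle 1, and independent, uniform event times. A DLT patient is then lost only if the event comes first, with probability q/2:

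expected rate ≈ 0.25(1 − q/2) / [0.25(1 − q/2) + 0.75(1 − q)]

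- q = 5%: 0.24375 / (0.24375 + 0.7125) = 0.255
- q = 10%: 0.2375 / (0.2375 + 0.675) = 0.260
- q = 15%: 0.23125 / (0.23125 + 0.6375) = 0.266

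The values of q are assumed; the documents give none. The shift is small and conservative, and the sponsor should accept it knowingly.
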